## **8.1 STUDY APPROVAL, SUBJECT INFORMATION, AND INFORMED CONSENT**

This trial will be initiated only after all required legal documentation has been reviewed and approved by the respective Institutional Review Board (IRB) / Independent Ethics Committee (IEC) and competent authority (CA) according to national and international regulations. The same applies for the implementation of changes introduced by amendments.

Prior to a subject's participation in the trial, written informed consent must be obtained from each subject (or the subject's legally accepted representative) according to ICH GCP and to the regulatory and legal requirements of the participating country. Each signature must be personally dated by each signatory and the informed consent and any additional subject information form are to be retained by the investigator as part of the trial records. A copy of the signed and dated written informed consent and any additional subject information must be given to each subject or the subject's legally accepted representative.

The subject must be informed that his/her personal trial-related data will be used by Boehringer Ingelheim in accordance with the local data protection law. The level of disclosure must also be explained to the subject.

The subject must be informed that his or her medical records may be examined by authorised monitors (Clinical Monitor Local/Clinical Research Associate) or Clinical Quality Assurance auditors appointed by Boehringer Ingelheim, by appropriate IRB/IEC members, and by inspectors from regulatory authorities.

## **8.2 DATA QUALITY ASSURANCE**

A quality assurance audit/inspection of this trial may be conducted by the sponsor or sponsor's designees, by IRBs/IECs, or by regulatory authorities. The quality assurance auditor will have access to all medical records, the investigator's trial-related files and correspondence, and the informed consent documentation of this clinical trial.

The data management procedures to ensure the quality of the data are described in detail in the trial data management and analysis plan (TDMAP) available in the trial master file.

## **8.3 RECORDS**

CRFs for individual subjects will be provided by the sponsor. For drug accountability, refer to [Section 4.1.8](#).

### **8.3.1      Source documents**

Source documents provide evidence for the existence of the subject and substantiate the integrity of the data collected. Source documents are filed at the investigator's site.

All data reported in the CRFs must be consistent with the source data or the discrepancies must be explained.

The investigator may need to request previous medical records or transfer records, depending on the trial.

### **8.3.2      Direct access to source data and documents**

The investigator/institution will permit trial-related monitoring, audits, IRB/IEC review and regulatory inspection, providing direct access to all related source data/documents. CRFs and all source documents, including progress notes (if applicable) and copies of laboratory and medical test results must be available at all times for review by the sponsor's clinical trial monitor, auditor and inspection by health authorities (e.g. FDA). The Clinical Research Associate/on site monitor and auditor may review all CRFs, and written informed consents. The accuracy of the data will be verified by reviewing the documents described in Section 8.3.1.

### **8.3.3      Storage period of records**

Trial site:

The trial site must retain the source and essential documents (including ISF) according to the national or local requirements (whatever is longer) valid at the time of the end of the trial.

Sponsor:

The sponsor must retain the essential documents according to the sponsor's SOPs.

## **8.4           EXPEDITED REPORTING OF ADVERSE EVENTS**

BI is responsible to fulfil their legal regulatory reporting obligation and in accordance to the requirements defined in this CTP.

## **10. APPENDICES**

Not applicable.

Proprietary confidential information © 2017 Boehringer Ingelheim International GmbH or one or more of its affiliated companies

## **11. DESCRIPTION OF GLOBAL AMENDMENT(S)**

This is the original protocol.

Number of global amendment		
Date of CTP revision		
EudraCT number		
BI Trial number		
BI Investigational Product(s)		
Title of protocol		
<hr/>		
To be implemented only after approval of the IRB / IEC / Competent Authorities		
To be implemented immediately in order to eliminate hazard – IRB / IEC / Competent Authority to be notified of change with request for approval		
Can be implemented without IRB / IEC / Competent Authority approval as changes involve logistical or administrative aspects only		
<hr/>		
Section to be changed		
Description of change		
Rationale for change		

2. LIST OF ABBREVIATIONS

Include a list of all abbreviations used in the Trial statistical analysis plan (TSAP)

Term	Definition / description
AE	Adverse event
BMI	Body mass index
CTP	Clinical Trial Protocol
DE	Dabigatran etexilate
EOT	End of treatment
ICH	International Conference on Harmonisation
MedDRA	Medical Dictionary for Regulatory Activities
PK	Pharmacokinetics
PKS	Pharmacokinetic set
PV	Protocol violation
REP	Residual effect period
RPM	Report planning meeting
SD	Standard deviation
TS	Treated set
TSAP	Trial statistical analysis plan

3. INTRODUCTION

As per International Conference on Harmonisation (ICH) E9, the purpose of this document is to provide a more technical and detailed elaboration of the principal features of the analysis described in the protocol, and to include detailed procedures for executing the statistical analysis of the primary and secondary variables and other data.

This TSAP assumes familiarity with the Clinical Trial Protocol (CTP), including Protocol Amendments. In particular, the TSAP is based on the planned analysis specification as written in CTP Section 7 “Statistical Methods and Determination of Sample Size”. Therefore, TSAP readers may consult the CTP for more background information on the study, e.g., on study objectives, study design and population, treatments, definition of measurements and variables, planning of sample size, randomisation.

SAS[®] Version 9.4 will be used for all analyses.

4. CHANGES IN THE PLANNED ANALYSIS OF THE STUDY

The intragastric pH of dabigatran will be explored descriptively.

If there are subjects with considerable high gastric pH, i.e. gastric pH values greater than 5.5 at baseline [\(1\)](#) in reference treatment (dabigatran etexilate alone), ANOVA analyses of primary and secondary endpoints (for the model refer to CTP 7.1.3) will in addition be conducted separately for subjects with considerable high gastric pH at baseline and subjects excluding considerable high gastric pH at baseline as appropriate with respect to number of subjects in the respective groups.

5. ENDPOINTS

5.1 PRIMARY ENDPOINTS

There is no primary endpoint for efficacy. The primary endpoints will be used as defined in the CTP, Section 5.5.1.1 as PK endpoints.

[figure not shown]
5.2 SECONDARY ENDPOINTS

[figure not shown]
5.2.1 Key secondary endpoints

There are no key secondary endpoints in this trial.

5.2.2 Other secondary endpoints

The other secondary endpoints will be used as defined in the CTP, Section 5.5.1.2.

6. GENERAL ANALYSIS DEFINITIONS

6.1 TREATMENTS

6.1.1 Treatment regimens / study intervals

There will be 7 phases in this trial:

screening, treatment period (dabigatran (Period 1), washout, rabeprazole (Period 2) and dabigatran + rabeprazole (period 2)), post-treatment, and post-study.

The treatment regimens/intervals in which a subject can lie during the course of the trial are defined as [Table 6.1.1: 1](#).

Table 6.1.1: 1 Treatment regimens/Intervals.

Label	Sort order	Start date (CRF)	Start time (CRF/derived)
Screening	00	Date of informed consent	0:00
dabigatran (Period 1)	01	Date of administration in Period 1	Time of administration in Period 1
Washout	02	Date of administration in Period 1	Time of administration in Period 1 + 1 minute
rabeprazole (Period 2)	03	Date of first administration of rabeprazole in Period 2	Time of first administration of rabeprazole in Period 2
dabigatran + rabeprazole (Period 2)	04	Date of first administration of dabigatran in Period 2	Time of first administration of dabigatran in Period 2
Post-treatment	05	Date of last administration in Period 2	Time of last administration in Period 2 + 1 minute
Post-study	99	Date of EOT + 1	0:00

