### **7.3.3 Safety analyses**

Safety will be assessed for the endpoints listed in [Section 5.2.1](#). All treated subjects (that is, all subjects who received at least one dose of study drug), will be included in the safety analysis. Safety analyses will be descriptive in nature and will be based on BI standards. No hypothesis testing is planned.

The analyses will be done by 'treatment at onset'.

Treatments will be compared in a descriptive way. Tabulations of frequencies/proportions will be used for the evaluation of categorical (qualitative) data, and tabulations of descriptive statistics will be used to analyse continuous (quantitative) data.

Measurements (such as ECG, vital signs, or laboratory parameters) or AEs will be assigned to treatments (see [Section 4.1](#)) based on the actual treatment at the planned time of the measurement or on the recorded time of AE onset (concept of treatment emergent AEs).

Therefore, measurements planned or AEs recorded prior to first intake of trial medication will be assigned to 'screening', those between first trial medication intake until next intake or the end of trial visit will be assigned to the preceding treatment, and those after the end of trial examination will be assigned to 'post-study'. Therefore, measurements planned or AEs recorded prior to first intake of trial medication will be assigned to 'screening', those between first trial medication intake until end of trial (see [5.2.2.2](#)) will be assigned to the treatment period. Events after the residual effect period but prior to next intake or end of trial examination will be summarized as 'post-treatment', those after the end of trial examination will be assigned to 'post-study'. These assignments including the corresponding time intervals will be defined in detail in the TSAP.

AEs will be coded using the Medical Dictionary for Regulatory Activities (MedDRA). Frequency, severity and causal relationship of AEs will be tabulated by treatment, system organ class and preferred term. SAEs and other significant AEs (according to ICH E3) will be listed separately.

Laboratory data will be compared to their reference ranges. Values outside the reference range as well as values defined as clinically relevant will be highlighted in the listings. Additionally, differences from baseline will be evaluated.

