7.8.1 Adverse events

AEs will be coded with the most recent version of MedDRA. The analyses of AEs will be descriptive in nature. All analyses of AEs will be based on the number of subjects with AEs and not on the number of AEs.

For analysis of AE attributes such as duration, severity, etc. multiple AE occurrence data on the CRF, will be collapsed into AE episodes provided that all of the following applies:

- The same MedDRA lowest level term was reported for the occurrences
- The occurrences were time-overlapping or time-adjacent (time-adjacency of 2 occurrences is given if the second occurrence started on the same day or on the day after the end of the first occurrence)
- Treatment did not change between the onset of the occurrences OR treatment changed between the onset of the occurrences, but no deterioration was observed for the later occurrence

For further details on summarisation of AE data, please refer to ([5](#), [6](#)).

The residual effect period (REP) for Dabigatran etexilate (DE) is defined as 3 days after the last administration of DE. Therefore, all AEs which occurred through the treatment phase and throughout the REP are considered as treatment emergent.

The analysis of AEs will be based on the concept of treatment emergent AE. That means that all AEs occurring between the first intakes of dabigatran till 3 days after will be assigned to treatment “dabigatran” (or “reference”) in period 1. In period 2 all AEs occurring between the first intake of rabeprazole until before the intake of dabigatran will be assigned to “rabeprazole“, then after the intake of dabigatran until 3 days later to “dabigatran+ rabeprazole” or “test”. AEs occurring after “dabigatran” but after the REP in period 1 will be assigned to ‘washout’. AEs occurring after “dabigatran+ rabeprazole” but before EOT will

be assigned to 'post-treatment'. All AEs occurring before first drug intake will be assigned to 'screening' and all AEs occurring after EOT will be assigned to 'post-study'.

According to ICH E3 (7), AEs classified as 'other significant' needs to be reported and will include those non-serious with

- (i) 'action taken = discontinuation' or 'action taken = reduced', or
- (ii) marked haematological and other lab abnormalities or lead to significant concomitant therapy as identified by the Clinical Monitor/Investigator at a RPM/database lock (DBL) meeting.

An overall summary of AEs will be presented.

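### SAP Table 6.1.1: 1 ends each dabigatran interval one minute after dosing, while SAP 7.8.1 keeps adverse events in the dabigatran treatment for three days

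*SAP*

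**What the plan says.** SAP 6.1.1 introduces its table with the words "The treatment regimens/intervals in which a subject can lie during the course of the trial are defined as" Table 6.1.1: 1. The table has start dates and start times but no end column. The dabigatran (Period 1) row starts at dosing. The washout row starts on the same date at "Time of administration in Period 1 + 1 minute". The dabigatran + rabeprazole row starts at DE dosing in Period 2, and the post-treatment row starts at "Time of last administration in Period 2 + 1 minute".

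SAP 7.8.1 gives a different rule for AEs. It sets the REP at three days after the last DE dose. For Period 1, "all AEs occurring between the first intakes of dabigatran till 3 days after will be assigned to treatment" dabigatran, and events after dabigatran "but after the REP in period 1 will be assigned to" washout. "In period 2 all AEs occurring between the first intake of rabeprazole until before the intake of dabigatran will be assigned to" rabeprazole; events from the DE intake until three days later then go to dabigatran + rabeprazole. SAP 7.8.2 defines the last on-treatment laboratory value by these treatment periods and refers to 7.8.1.

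Protocol 5.2.2.2 has the same three-day REP and counts AEs within it as on treatment. Protocol 7.3.3 leaves the detailed intervals to the SAP, and its own text contains two versions. In one, "those between first trial medication intake until next intake or the end of trial visit will be assigned to the preceding treatment". In the other, "Events after the residual effect period but prior to next intake or end of trial examination will be summarized as" post-treatment.

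**The concern.** The SAP is the document charged with fixing these intervals, and it gives the same labels two different start points. A programmer who derives the analysis period from the section said to define it would get a one-minute DE interval in each period.

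Three outputs or rules depend on the labels:

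- **AE frequency table.** The table by system organ class and preferred term has dabigatran, rabeprazole and dabigatran + rabeprazole columns. Under Table 6.1.1: 1, nearly all DE-period events would move to washout or post-treatment and leave the two DE columns.
- **On-treatment laboratory values.** The 24 h sample is the only scheduled post-dose laboratory test within each period (protocol Flow Chart). Under Table 6.1.1: 1 it would not be on treatment.
- **AE episodes.** SAP 7.8.1 collapses repeated occurrences partly according to whether treatment changed between onsets, so an undefined treatment also affects that step.

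A second gap remains even if 7.8.1 governs. On the planned schedule rabeprazole starts before the Period 1 REP has ended, and the SAP does not say which treatment then takes the event.

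**Working it through.** The plan states no figure to reproduce, so the check lays each rule on the planned clock, in hours from the first DE dose.

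**Inputs**

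- First DE dose: Visit 2 Day 1, 10:00 (protocol Flow Chart).
- First rabeprazole dose: 06:00 (protocol 4.1.4) on the day after Visit 2 Day 3 (Flow Chart footnote 4), that is, 06:00 on the fourth day.
- Second DE dose: 100 h after the first rabeprazole dose (Flow Chart, −100:00).
- Last rabeprazole dose: 4 h before the second DE dose (Flow Chart footnote 5). The last administration in Period 2 is therefore DE.
- REP: three days, taken as 72 h (SAP 7.8.1; protocol 5.2.2.2).
- End-of-trial visit: 5 to 14 days after Visit 3 Day 1 (Flow Chart).

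**Timeline**

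- First rabeprazole dose: 10:00 on Day 1 to 10:00 on Day 3 is 48 h, and to 06:00 the next morning is 20 h more, so 48 + 20 = 68 h.
- Second DE dose: 68 + 100 = 168 h.
- End-of-trial visit: 5 × 24 = 120 h to 14 × 24 = 336 h after the second DE dose.

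**Interval lengths under each rule**

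| Rule | DE interval, Period 1 | Planned washout | DE interval, Period 2 |
|---|---|---|---|
| SAP Table 6.1.1: 1, rows read consecutively | 1 min | 68 h − 1 min = 67 h 59 min | 1 min |
| SAP 7.8.1 | 72 h (68 h if rabeprazole takes precedence) | 0 h, since 72 > 68 | 72 h |
| Protocol 7.3.3, until next intake or end-of-trial visit | 68 h if rabeprazole counts as trial medication, 168 h if only DE does | not used | about 120 to 336 h |
| Protocol 7.3.3, REP version | 72 h, subject to the same overlap | not used | 72 h |

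**Gap between the two SAP rules:** 72 h − 1 min = 71 h 59 min in each period. The twelve scheduled post-dose blood samples, from 0:30 to 48:00, show the scale: all twelve times fall after the table's boundary and inside the 7.8.1 window. Neither protocol version supports a boundary at one minute.

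**Overlap within SAP 7.8.1:** 72 − 68 = 4 h, which is 4/72 = 5.6% of the Period 1 REP. An onset in that window meets both the dabigatran rule and the rabeprazole rule.

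**The case against.** The strongest defence is that the table and 7.8.1 work in two layers. SAP 7.8.1 and protocol 5.2.2.2 both speak of the treatment phase and then the REP, so the table could be listing dosing intervals for a single-dose drug, to which the AE section adds three days. No analysis section cites the table. The AE frequency table sits in the section that states the three-day rule, and the laboratory section refers to that section by number. This stands in part: the intended rule can be recovered, and harm requires someone to program from the table. But no text describes two layers, and the reading does not explain why washout and post-treatment each have two start points.

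On the overlap, it can be argued that rabeprazole clearly takes over. SAP 7.8.1 is organised by period, the table starts the rabeprazole row at first intake, and one protocol sentence runs to the next intake. These points favour that answer without settling it. Protocol 4.1.1 lists rabeprazole as a non-investigational or auxiliary product, a differing version follows the next-intake sentence, and protocol 6.2.2 even labels Visit 3 Day −4 as Period 1.

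The overlap is also likely to hold few events. The earlier tablet trial reported two AEs in 35 subjects (protocol 1.2) and had six periods (protocol 9.2). Assuming all periods were completed and onsets are uniform over 72 h, the expected number here is 36 × 2/(35 × 6) × 4/72 ≈ 0.02. Events due to rabeprazole or the pH sensor could add to that. The point about size stands, but a rule is still needed for any event that does occur.

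Vital signs are summarised by planned visit, ECG data are not listed and exposure is only a listing, so none of these depends on the table.

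**Conclusion.** The point holds. The SAP contains two incompatible sets of boundaries for the same labels, 71 h 59 min apart in each period. The set said to define the intervals disagrees with SAP 7.8.1 and with the protocol's three-day REP. In addition, 7.8.1 leaves a 4 h window (68 to 72 h, 5.6% of the Period 1 REP) assigned to two treatments, and it leaves washout empty on the planned schedule although 6.1.1 counts it as one of seven phases.

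The one-minute figure assumes that each table row ends where the next begins, because no end times are given. The 68 h and 4 h figures assume planned clock times and three days equal to 72 h. A calendar-day reading would change the overlap but not the conflict over the one-minute start.

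The consequence is limited to descriptive attribution of AEs and on-treatment laboratory values. All AEs are still listed, and the other planned AE tables are not stated to be restricted to the three treatment columns. This should be fixed because the correction is very cheap and the table as written would misattribute almost everything after dosing.

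**What to change.** In SAP Table 6.1.1: 1:

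- Start post-treatment at the Period 2 DE dose plus three days.
- Start washout at the Period 1 DE dose plus three days, and only if that time precedes the first rabeprazole intake. Note that the phase is expected to be empty for subjects on the planned schedule.

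Add one precedence sentence for the overlap. For example, onsets from the first rabeprazole intake go to rabeprazole, which agrees with the table's existing start for that row and with the protocol's next-intake wording. State whether three days means 72 h or calendar days. Use the same boundaries in 6.1.1, 7.8.1 and 7.8.2.

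Under that precedence rule the Period 1 DE column covers 68 h and the Period 2 column 72 h; a footnote saying so is optional.

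A single sentence making 7.8.1 govern AE and laboratory attribution would remove the main conflict, but not the overlap, and it would leave the misleading start times in the table.

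The cost is a few table cells, a sentence or two in the SAP and a check of the interval derivation in the programs. No protocol change is needed, and subjects are not affected.

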6.2 IMPORTANT PROTOCOL VIOLATIONS

Data discrepancies and deviations from the CTP will be identified for all subjects in the database (i.e., treated subjects and subjects with serious AE (SAE) which the investigator considered related to the screening procedure). Consistency check listings (for identification of violations of time windows) and a list of protocol deviations (e.g. deviations in drug administration, in blood sampling times, etc.) will be provided to be discussed at the report planning meeting (RPM). At this meeting, it will be decided whether a discrepant data value can be used in analyses or whether it must be corrected in the clinical database.

Each protocol deviation must be assessed to determine whether it is an important protocol violation (PV). For definition of important PVs, and for the process of identification of these, refer to the Boehringer Ingelheim reference document 'Protocol Violation Handling Definitions' ([2](#)).

If any important PVs are identified, they are to be summarised into categories and will be captured in the RPM minutes via accompanying Excel spreadsheet ([3](#)). The following table contains the categories which are considered to be important PVs in this trial. If the data show other important PVs, this table will be supplemented accordingly by the time of the RPM. If substantial numbers of PVs are reported at the RPM, a decision about summarising the PVs in a tabular format will be made. Otherwise, only a PV listing will be provided.

The following [Table 6.2: 1](#) gives the important PVs for this trial.

Table 6.2: 1 Important PVs

Category /Code	Description	Requirements/Comment	Excluded from
A	Entrance criteria not met		
A1	Inclusion criteria violated	Inclusion criteria No.1, 2 and 3 Automatically detectable.	None
A2	Exclusion criteria violated	Automatically detectable.	PKS
B	Informed consent		
B1	Written Informed consent not given	Inclusion criteria No.4 Automatically detectable.	All
B2	Informed consent too late	Informed consent date was after screening visit. Automatically detectable.	None
C	Trial medication and randomisation		
C1	Non-compliance with trial medication	No trial drug administration. Automatically detectable.	TS and PKS
C2	Incorrect trial medication taken	Manually detectable.	None
C3	Incorrect intake of trial medication	Manually detectable.	PKS
C4	Improper washout between treatments	Washout period has to be more than 3 days. Automatically detectable	PKS
D	Concomitant medication		
D1	Administration of any drugs and/or intake of any foods which might influence the results of PK	For example; Administration of any drugs before or during the trial Violation of restricted lifestyle Manually detectable.	PKS
E	Missing data		
E1	Certain violations of procedures used to measure primary or secondary data	Violations of procedures which may lead to invalid measurements with respect to primary or secondary PK endpoints. Manually detectable.	PKS
F	Incorrect timing		
F1	Certain violations of time schedule used to measure primary or secondary data	PK sample taken too early/too late. Manually detectable.	PKS

KEY: TS = Treated set, PKS = Pharmacokinetic set

